5.3 Run-in Procedures

There is no run-in phase for this study.

5.4 Contraindications

While taking the study agent the participant should be instructed not to take any:

- Strong CYP3A4 inhibitors including: ketoconazole, atazanavir, boceprevir, ceritinib, clarithromycin, cobicistat; darunavir, dasabuvir, idelalisib, indinavir, itraconazole, lopinavir, nefazodone, nelfinavir, ombitasvir, paritaprevir, posaconazole, ritonavir, saquinavir, telaprevir, telithromycin, troleandomycin, voriconazole, and grapefruit or grapefruit juice.
- CYP3A4 inducers including: rifampicin, rifabutin, rifapentine, phenytoin, carbamazepine, phenobarbital, primidone, enzalutamide, fosphenytoin, lumacaftor, mitotane, and St. John's Wort. Avoid the use of other antacids if possible. NSAIDs with the exception of ≤ 81 mg aspirin per day. Acetaminophen may be used as needed.
- Participants should be instructed not to consume grapefruit or drink any beverages containing grapefruit juice.

5.5 Concomitant Medications

Erlotinib is protein bound (92–95%) in humans and metabolized in the liver by CYP3A4 and, to a lesser extent, CYP1A2, and in the lungs by CYP1A1. A potential for drug-drug interaction exists when erlotinib is coadministered with drugs that are highly protein bound or that are potent CYP3A4 inhibitors/inducers. Potent inducers of CYP3A4 activity increase erlotinib metabolism and significantly decrease erlotinib plasma concentrations, while strong CYP3A4 inhibitors increase exposure to erlotinib. For patients who are being concomitantly treated with a strong CYP3A4 inhibitor, a dose reduction should be considered in the presence of severe AEs. For patients who are being concomitantly treated with a potent CYP3A4 inducer, alternative treatments that lack potent CYP3A4-inducing properties should be considered.

Drugs that alter the pH of the upper GI tract may alter the solubility of erlotinib and reduce its bioavailability. Coadministration of erlotinib with omeprazole, a proton pump inhibitor, decreased the erlotinib exposure and maximum concentration by 46% and 61%, respectively (Kletzl 2015); therefore, participants that use proton pump inhibitors concomitantly with erlotinib will be stratified to account for the decreased erlotinib exposure.

Altered coagulation parameters and infrequent reports of bleeding events, including gastrointestinal and non-gastrointestinal bleeding, have been reported in patients in erlotinib clinical studies, some associated with concomitant warfarin administration. Patients taking warfarin or other coumadin-derivative anticoagulants should be closely monitored for changes in prothrombin time and International Normalized Ratio (INR).

All medications (prescription and over-the-counter), vitamin and mineral supplements, and/or herbs taken by the participant will be documented on the concomitant medication CRF and will include start and stop dates, dose frequency and indication. Medications taken for a procedure (*e.g.*, biopsy) should also be included. Medications given in the hospital as part of the standard surgical protocol will not be documented as concomitant medications. However, any medications given to treat an adverse or unexpected event following surgery will be documented.

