Participants for this protocol will be accrued from a population of males and females 18 years of age and older who have a confirmed or suspected bladder tumor which will be treated with TURBT (or planned cystoscopy with biopsies) or cystectomy (total or partial). Eligible participants will be randomly assigned to either 600 mg erlotinib PO or matching placebo once weekly for 3 doses preceding their scheduled bladder surgery. The study will be terminated when all participants have completed study dosing, their scheduled surgical treatment, and a 7-14 day post-surgery follow-up period.

There is no run-in period specified for this protocol. Potential study participants will be identified from the population of patients being evaluated and treated for bladder tumors at each of the participating institutions. After being presented with information about the protocol, patients interested in participating will be scheduled for a screening/baseline study visit. After completion of the informed consent process, the following assessments/procedures will be conducted:

Screening/Baseline visit (within 30 days of first dose of study agent):

- eligibility assessment
- medical/surgical history and baseline symptoms
- physical exam/vital signs (including performance status assessment)
- clinical safety labs (including pregnancy testing for females of childbearing potential)
- plasma pharmacokinetics
- request for randomization
- International Prostate Symptom Score (I-PSS)

Study agent and topical ointment (topical clindamycin, topical hydrocortisone) dispensing: (within 30 days of baseline assessments) either in clinic or study agent will be mailed to the participant via overnight courier with a phone contact prior to dosing. Ointment instructions will be included (See Appendix B).

- study agent dosing instructions
- ointment instructions
- concomitant medication review and adverse event assessment

Pre Day 8 Phone contact (approximately 24-72 hours prior to Day 8 Visit):

- instruct participant on dose and time of Day 8 study drug administration

Day 8 Visit*:

- physical exam/vital signs (including complete assessment of any rash per CTCAE criteria)
- clinical safety labs
- plasma pharmacokinetics
- Day 8 Study dosing after plasma pharmacokinetics
- concomitant medication review, compliance and adverse event assessment

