4.2 Exclusion Criteria

4.2.1 Any treatment for the bladder tumor other than intravesical therapy between the pre-study cystoscopy or radiologic imaging which identified the suspected bladder tumor and the scheduled surgical removal or cystoscopy-guided biopsy of that tumor.

4.2.2 Any chemotherapy and/or radiation therapy received ≤ 3 months of study entry and any immunotherapy received ≤ 6 months of study entry (with the exception of BCG treatment).

4.2.2.1 Any prior external beam radiation to the pelvis.

4.2.3 A concurrent skin rash or skin condition requiring treatment with a prescription medication.

4.2.4 The following medications may not be taken within 24 hours of the first dose of study agent or at any time while a participant is taking study agent due to the risk of significant drug-drug interaction.

- Coumadin
- Strong CYP3A4 inhibitors (which lead to decreased erlotinib metabolism/increased erlotinib levels) including ketoconazole, atazanavir, boceprevir, ceritinib, clarithromycin, cobicistat, darunavir, dasabuvir, idelalisib, indinavir, itraconazole, lopinavir, nefazodone, nelfinavir, ombitasvir, paritaprevir, posaconazole, ritonavir, saquinavir, telaprevir, telithromycin, troleandomycin, voriconazole, and grapefruit or grapefruit juice.
- CYP3A4 inducers (which lead to increased erlotinib metabolism/decreased erlotinib levels) including rifampicin, rifabutin, rifapentine, phenytoin, carbamazepine, phenobarbital, primidone, enzalutamide, fosphenytoin, lumacaftor, mitotane, and St. John's Wort.
- Agents which decrease gastric acid are allowed but should be avoided if possible.
- Participants may resume inhibitors or inducers of CYP3A4 > 14 days after their last dose of study agent

4.2.5 Participants requiring daily use of non-steroidal anti-inflammatory drugs (NSAIDs), with the exception of ≤ 81 mg aspirin per day. During study participation, acetaminophen is preferred for treatment of pain; the use of NSAIDs, as needed for pain, is discouraged.

4.2.6 Participants may not be receiving any other investigational agents.

4.2.7 History of allergic reactions attributed to compounds of similar chemical or biologic composition to erlotinib or clindamycin (topical agent for potential skin toxicity).

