study visits and procedures with the participant. The participant should be provided a study calendar to record any side effects and the time the participant takes their study medication. The participant should be strongly encouraged to contact the research staff with questions about study participation.

Randomization and Drug Request

Once the eligibility evaluations have been completed and the participant meets all of the inclusion criteria in section 4.1 and meets none of the exclusion criteria in section 4.2, then the participant may be randomized to the trial. Before the participant may be randomized, the Eligibility Checklist must be completed and signed. Refer to section 6.8 for specific instructions on participant randomization.

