- Swelling, irritation, or scarring of the lungs, which may cause pain or difficulty breathing.
- A tear or hole in the stomach that may require surgery. More common in people with ulcers (sores in the stomach), diverticulitis (redness, pain, and swelling of part of the belly), and in people who take some types of drugs (NSAIDS, corticosteroids, chemotherapy). Talk to your study doctor about drugs to avoid.
- Severe blistering or peeling of the skin
- Patches of skin may become darker in color
- Redness, swelling, sores, or a tear or hole in eye which may cause pain or blurred vision.
- Increased bleeding (Internal bleeding, nose bleed). More common in people who take blood thinning drugs.
- Increased body hair growth, hair loss, eyelash/eyebrow changes, or brittle/loose fingernails or toenails
- Severe diarrhea or vomiting can cause an imbalance of minerals in the blood (called electrolytes) such as low potassium, with symptoms that may include weakness, fatigue, muscle cramps, or constipation.
- In people with cancer of the pancreas who took combined treatment of erlotinib plus gemcitabine: heart attack, stroke, decreased red blood cells (anemia) which may cause tiredness, or may require blood transfusion, and decreased platelets which may cause easy bleeding, or longer bleeding.

Special Concerns

Erlotinib can interact with some kinds of antibiotics, antiviral, and antifungal drugs, and warfarin (a blood thinner). You should make sure you have told your cancer doctor about all medicines you are using, and make sure your local doctor knows you are taking erlotinib if they prescribe any new ones.

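### Section 4.2.4 bans Coumadin and strong CYP3A4 inhibitors throughout dosing, but section 5.5 tells sites how to manage patients taking them, and the do-not-take list in 5.4 omits Coumadin

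*Combined protocol and SAP*

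**What the plan says.** Four parts of the combined protocol and SAP bear on this.

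- **4.2.4 (Exclusion Criteria)** lists Coumadin, strong CYP3A4 inhibitors and CYP3A4 inducers. They are barred from 24 hours before the first dose "or at any time while a participant is taking study agent due to the risk of significant drug-drug interaction". This is a rule of conduct during dosing as well as an entry criterion. It adds, for the CYP3A4 drugs only, "Participants may resume inhibitors or inducers of CYP3A4 > 14 days after their last dose of study agent".
- **5.4 (Contraindications)** opens "While taking the study agent the participant should be instructed not to take any" and then names strong CYP3A4 inhibitors, CYP3A4 inducers, NSAIDs and grapefruit. Neither Coumadin nor warfarin is on the list.
- **5.5 (Concomitant Medications)** says "Patients taking warfarin or other coumadin-derivative anticoagulants should be closely monitored for changes in prothrombin time" and INR. It also says "For patients who are being concomitantly treated with a strong CYP3A4 inhibitor, a dose reduction should be considered" when severe adverse events occur. For a potent inducer it advises considering alternative treatments. It does not refer to 4.2.4 or 5.4.
- **Appendix B** names warfarin as an interacting drug. It asks participants to tell their cancer doctor about all their medicines and to "make sure your local doctor knows you are taking erlotinib if they prescribe any new ones". It does not state the ban.

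At entry, 7.2 allows randomization only if the participant "meets none of the exclusion criteria in section 4.2", with a signed checklist, and 6.8 has the lead organization verify eligibility. At dispensing, section 3 schedules a "concomitant medication review and adverse event assessment".

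**The concern.** When a concomitant drug turns up, site staff are likely to open 5.5. For warfarin, 5.5 says to monitor and does not say to stop. For a strong inhibitor, it says to consider a lower dose if there are severe adverse events. Under 4.2.4 neither combination is allowed at all. For warfarin, 5.4 does not correct the impression, because Coumadin is missing from it.

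The stakes are mainly safety. Section 5.5 itself notes bleeding events with erlotinib, some with concomitant warfarin, and under 5.2 the last dose comes about 9-18 hours before TURBT or cystectomy. A strong inhibitor also raises erlotinib exposure, which the trial measures and which 13.4 plans to relate to the primary marker through a measure of dose received.

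**Working it through.** **Step 1. Compare the rules drug by drug.**

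| Drug group | 4.2.4 | 5.4 | 5.5 | Conflict |
|---|---|---|---|---|
| Coumadin/warfarin | Banned throughout dosing | Not listed | Monitor PT/INR | Yes; the ban is stated once only |
| Strong CYP3A4 inhibitors | Banned throughout dosing | Banned | Consider dose reduction for severe AEs | Yes |
| CYP3A4 inducers | Banned throughout dosing | Banned | Consider alternatives (potent inducers) | No; same direction, but advisory |

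**Step 2. Is 5.5 supported elsewhere?** The schedule of events (7.1) and the end-of-study laboratory list (7.4) contain no PT or INR. Section 5.6 already requires a 50% reduction for any adverse event of grade 3 or higher, so the advice to consider one for severe events adds little and is weaker than the rule in force.

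**Step 3. Who could be affected?** The checklist, the lead-organization check and the medication reviews at baseline and dispensing should catch current users. That leaves a drug started, or resumed after a pause, during dosing. The last scheduled medication review before the final dose is at the day 8 visit or, if that visit is skipped, by phone within 48 hours of the day 8 dose, so day 8 to day 10. The shortest gap is the earliest final-dose day minus 10; the longest is the latest minus 8.

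| Surgery | Final dose | Gap to final dose (days) |
|---|---|---|
| Day 16 | Day 15 | 15 − 10 = 5 to 15 − 8 = 7 |
| Day 17-22 | Day 16-21 | 16 − 10 = 6 to 21 − 8 = 13 |
| Day 23-28 | Day 22-27 (fourth dose) | 22 − 10 = 12 to 27 − 8 = 19 |

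The next scheduled review is at the surgery visit, after the last dose. The pre-surgery reminder call is 24-72 hours before surgery and the final dose 9-18 hours before, so the call precedes that dose by 24 − 18 = 6 to 72 − 9 = 63 hours. A question asked there would come in time.

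**Step 4. Statistical cost of enforcing the ban.** Section 13.3 uses a two-sided two-sample t-test, alpha 0.05, effect size 1, with 14 placebo and 28 erlotinib participants needed and 15 and 30 enrolled. The noncentrality is the square root of n1·n2/(n1 + n2), with n1 + n2 − 2 degrees of freedom.

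- 14/28: noncentrality 3.055, 40 df, power 0.846. This reproduces the stated 0.85.
- 14/27 (one further erlotinib loss): 3.036, 39 df, power 0.842.
- 13/28 (one further placebo loss): 2.980, 39 df, power 0.828.

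The enrolment margin is 15 − 14 = 1 placebo and 30 − 28 = 2 erlotinib participants. It is already allotted to dropout: up to 5% in 13.3 and 5-10% in section 3, which is 2.25 to 4.5 of 45.

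**The case against.** The best defence is that 5.5 is general drug-interaction background and that 4.2.4, an explicit prohibition, plainly prevails. No PT/INR is scheduled, 5.6 already forces dose reduction for severe events, and 8.3 lists concomitant medications and medical contraindication among the reasons for stopping agent. On this view 5.5 creates no working route to co-administration.

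That is a fair account of what was probably intended, but the text does not say it. The disputed sentences tell staff what should be done for patients, and the same section sets trial rules such as stratification for proton pump inhibitor use and recording of medications. Nothing limits them to background or inadvertent use. Section 8.3 says participants may stop; 5.5 does not point there.

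Several limiting points do stand. A reader might infer any of the following, and the documents do not support them:

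- **That all three drug groups are in equal conflict.** The inducer advice points the same way as the ban, and both CYP3A4 classes are banned again in 5.4, immediately before 5.5.
- **That participants are never told of the warfarin ban.** Appendix B is largely a drug-information and side-effect sheet and states no CYP3A4 or grapefruit ban either. The consent pages are not available to check.
- **That a resumption time for Coumadin is missing.** On its wording the Coumadin ban ends with dosing; the 14-day line is an extra restriction on CYP3A4 drugs.
- **That the pre-surgery call covers dosing only.** Section 7.3 also mentions leftover drug and surgery-day appointments, and its list of dosing items is open-ended. It does not specify a medication review.

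**Conclusion.** The inconsistency is real and should be corrected. For warfarin and strong CYP3A4 inhibitors, 5.5 gives instructions that 4.2.4 does not allow. For warfarin, nothing outside the exclusion criteria repeats the ban and no scheduled test supports the monitoring. For inducers, 5.5 is only softer than the rule.

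The practical exposure is narrow: a drug started or resumed in the 5 to 19 days between the last scheduled medication review and the final dose, or before the day 8 dose in a participant who skips that visit, followed by a site acting on 5.5. The documents give no rate for this; that it is rare is an assumption, resting on entry screening and a dosing course of roughly two to four weeks.

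It would be wrong to conclude that the protocol permits warfarin with study agent, or that the primary comparison is compromised. Section 4.2.4 forbids the combination, and the conflict in wording changes neither alpha nor the planned sample size.

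**What to change.** Let 4.2.4 govern.

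1. Add Coumadin/warfarin to the do-not-take list in 5.4.
2. Replace the warfarin, strong-inhibitor and inducer sentences in 5.5 with a cross-reference to 4.2.4. State that study agent is not given while one of these drugs is being taken: substitute the other drug where clinically appropriate, otherwise stop agent under 8.3 with the participant remaining on study. The sponsor sets any interval before agent may restart; the 24 hours in 4.2.4 covers only the first dose.
3. Optional, and not needed to remove the contradiction: ask about new or resumed medications in the existing pre-surgery reminder call.

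The cost is a wording amendment, plus one question in a scheduled call if item 3 is adopted; no visit or test is added. The downside is that a participant who misses a dose becomes non-evaluable for the primary endpoint under 5.7.1, although 13.8 would keep that participant in the main analysis. The margin of 1 placebo and 2 erlotinib participants should not be treated as spare for this purpose. If 5.7.1 is applied, the power loss is that in Step 4 of the working, larger for a placebo loss than for an erlotinib loss.

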5.6 Dose Modification

Study drug will be dose reduced (by 50%) from 4 tablets to 2 tablets for any of the following events:

- A grade 1 rash or diarrhea that the study subject finds unacceptable and desires the 50% dose reduction.
- A grade 2 skin toxicity
- A grade 2 diarrhea that does not respond to Imodium
- Any toxicity or adverse event \geq grade 3
- MD discretion for side effects assessed as at least possibly related to the study drug and for which the study subject finds unacceptable and desires the 50% dose reduction

Subjects that meet the above dose modification criteria even after a dose reduction will not receive any further doses. At the first report of grade 1 or 2 skin toxicity, subjects should be instructed on using the dispensed topical ointments (1% Clindamycin, 1% hydrocortisone): apply twice daily (not at the same time) each ointment to the affected area only. Subjects who report grade 1 or 2 diarrhea likely to be attributable to study drug should be instructed to use loperamide (Imodium) 2 mg after each loose stool. Provide participants with a copy of Appendix B.

5.7 Adherence/Compliance

5.7.1 Compliance (tablet ingested/tablet instructed to take) will be assessed, but only subjects who take all study drug weekly for 3 doses (or 4 doses due to surgery delay) will be evaluable for the primary endpoint.

5.7.2 Compliance will be assessed via subject questioning, returned tablet count and planned drug levels.

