6.9 Blinding and Unblinding Methods

Unblinded study personnel will be the study statisticians, and the DCP Drug repository staff. No staff involved in patient care or assay performance and interpretation will be unblinded. All participants will be administered identical drug, so the study staff will be blinded to both the treatment and dose level. All drug will be dispensed and reordered according to kit number, and so the pharmacy staff will all remain blinded to treatment.

All requests to unblind treatment assignment will be funneled to the Consortium Principal Investigator [[name], [contact], [contact]]. [name] will determine if disclosure of treatment assignment is required after consultation with the NCI/DCP medical monitor ([name]) and/or the protocol chair ([name]) or the Data and Safety Monitoring Board. Except in cases of emergency, decisions regarding unblinding of the treatment group of a randomized subject will be made in consultation with the NCI/DCP medical monitor, [name]. If disclosure of the treatment would affect important medical decisions in a subject experiencing an adverse event, unblinding might be allowed. Other circumstances might warrant breaking the blind but the decision will be left to the [name] and the DSMB. Authorization for unblinding of randomized treatment will come from [name] or the DCP Medical Monitor. If disclosure is warranted, the site will be directed to the product label found in the subject's CRF binder or other designated research record. The label has a scratch off area that will disclose the treatment. The site will complete an Unblinding Disclosure Form and send it to the CLO [[name] or [contact]]. Each site will document the unblinding process in the patient chart.

The NCI Medical Monitor and/or Scientific Monitor will be notified that the blind has been broken.

[name]
Prostate and Urologic Cancer Research Group
Division of Cancer Prevention, National Cancer Institute, NIH, DHHS
Shady Grove Campus
[name]
[name]
[contact];
[contact]

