7.2 Baseline Testing/Prestudy Evaluation

Baseline Evaluations

Baseline evaluations determine if the participant is a fit candidate for study participation and establish the participant's health status before entering the study. Standard-of-care labs or procedures done prior to signing consent will qualify for these baseline evaluations (i.e. physical exams, routine labs, vital signs) provided they were obtained within 30 days of the participant's Day 1 dose of study agent. All baseline evaluations (including labs) must be completed before requesting randomization and dispensing study drug. An Eligibility Checklist will be provided by the CLO at study initiation to help determine if the participant is eligible for the trial. This document will need to be signed and submitted to the CLO at the time of randomization.

Baseline **cystoscopy** demonstrating a bladder tumor. The physician should assess if the bladder tumor is invasive or non-invasive. The baseline cystoscopy must be completed within 120 days of randomization.

At the screening/baseline visit, blood for pharmacokinetics may be collected before eligibility has been confirmed. However, if the participant is later found to be ineligible, the sample may not be used. If the participant is found to be ineligible, clearly document the destruction of the pharmacokinetic blood sample in the participant's research chart.

A review of the participant's **medical history** will be done within 30 days of randomization.

A **physical examination** must be performed within 30 days of randomization.

Performance Status, using the Karnofsky must be assessed

A review of **concomitant medications** will be done within 30 days of randomization.

Laboratory tests needed for eligibility are: WBC, platelets, hemoglobin, total bilirubin, AST, ALT, alkaline phosphatase, creatinine, sodium and potassium. All of these laboratory analyses must be completed within 30 days before randomization.

Women of child-bearing potential must have a negative pregnancy test within 30 days of randomization.

Plasma Pharmacokinetics - Levels of erlotinib and metabolites will be assessed for all participants.

International Prostate Symptom Score (I-PSS) – The participant will complete the survey within 30 days of randomization

Review of Study Participation and Study Calendar - The research staff should review the upcoming

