9. CORRELATIVE/SPECIAL STUDIES

9.1 Rationale for Methodology Selection

Erlotinib Pharmacokinetics. Pharmacokinetic parameters have been consistently associated with erlotinib toxicity, an important consideration in chemoprevention trials and will be assessed as part of this trial. (White, 2011, Lu 2006)

Blood samples will be collected prior to starting therapy, prior to dosing on day 8 (if available), and on the day of surgery, approximately day 16. Erlotinib and its principal metabolite OSI-420 will be evaluated by high-performance liquid chromatography as previously described (Hamilton 2006).

EGF receptor. EGF receptor (EGFR) is upregulated in most epithelial cancers where signaling through EGFR contributes to cancer cell proliferation and survival. The limited clinical efficacy of EGFR inhibitors suggests that identification of resistance mechanisms may identify new pathways for therapeutic targeting. E-Cadherin. Studies have shown that the extent of loss of E-cadherin was associated with the depth of urothelial carcinoma invasion (Sun 2002), and that E-cadherin plays a central role in modulation of EGFR response in urothelial carcinoma (Black 2008). Ki67. Antigen KI-67 is a nuclear protein that is associated with and may be necessary for cellular proliferation. Lubet et al. (Lubet 2013 submitted) observed decreased Ki67 expression in response to weekly erlotinib in the MNU mouse breast cancer model as well as a significant decrease in phosphorylated ERK expression. ERK. Extracellular regulated kinase (ERK) is an important downstream factor of EGFR in MAP kinase pathway. Its activation (phosphorylation) plays a key role in carcinogenesis and cancer progression of many cancers (Lujan 2010, Chou 2010) including urothelial carcinoma (Lee 2013, Ling 2011). Study showed that aberrant ERK activation causes resistance to some EGFR kinase inhibitors (Ercan 2012).

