13.6 Reporting and Exclusions

As the nature of this study is exploratory, intent-to-treat should not be used as a principal analysis criteria. Nevertheless, no subjects will be excluded from the analysis and reporting, except for obvious random dropouts and for those who never took the protocol treatment.

Compliance with the protocol treatment will be measured in the form of pill counts; the information will not be used for the primary analysis, but for the analysis supporting the primary endpoint. There will be no imputation of missing data for both the primary and the secondary endpoints.

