13.8 Evaluation of Outcome/Endpoints

For the primary analysis comparing EGFR phosphorylation across the treatment groups, the as-randomized analysis will be used. All of the participants who met the eligibility criteria, with the exception of those who did not receive study agent, will be included in the main analysis. Random dropouts will be excluded.

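### Erlotinib plasma level feeds into evaluability for the primary endpoint, although it can test intake in one arm only; this conflicts with 13.6 and 13.8, and the 6.9 blinding statement cannot hold for the pharmacokinetic laboratory

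*Combined protocol and SAP*

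**What the plan says.** The combined protocol and SAP gives two rules for who counts in the primary comparison.

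- **Section 5.7.** Under 5.7.1, "only subjects who take all study drug weekly for 3 doses (or 4 doses due to surgery delay) will be evaluable for the primary endpoint". Section 5.7.2 then says how intake is judged: "Compliance will be assessed via subject questioning, returned tablet count and planned drug levels".
- **Sections 13.6 and 13.8.** Section 13.6 says "Compliance with the protocol treatment will be measured in the form of pill counts", and the same sentence goes on: "the information will not be used for the primary analysis, but for the analysis supporting the primary endpoint". Of the main analysis, 13.8 says "All of the participants who met the eligibility criteria, with the exception of those who did not receive study agent, will be included in the" (the sentence ends by naming that analysis); it then removes random dropouts. Sections 13.1 and 13.4 call the comparison as-randomized.

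The only drug levels planned are erlotinib and its metabolite. Section 7.2 says "Levels of erlotinib and metabolites will be assessed for all participants". On timing, 9.1 says "Blood samples will be collected prior to starting therapy, prior to dosing on day 8 (if available), and on the day of surgery, approximately day" (the number that follows is 16). Section 7.4 places the surgery sample about 9-18 hours after the last dose, and the day 8 clinic visit is optional.

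On blinding, 6.9 lists the statisticians and the drug repository staff as unblinded and adds "No staff involved in patient care or assay performance and interpretation will be unblinded".

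No section says who receives the drug levels or when, what level counts as non-compliant, or who decides evaluability.

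**The concern.** A compliance measure that helps decide who enters a randomized comparison should work the same way in both arms. Plasma erlotinib does not. Someone on erlotinib who reports the last dose as taken but skipped it can be contradicted by an undetectable level. Someone on placebo who does the same cannot. If 5.7 is followed as written, the two arms are filtered by different tests after randomization.

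The measure also needs the treatment code. Read blind, an undetectable level would make every placebo participant look like a non-taker. So whoever applies 5.7.2 must know the assignment, while 6.9 keeps patient-care and assay staff blinded. The laboratory that measures erlotinib in everyone will in effect learn the arm from its own results.

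At stake are the make-up of the primary analysis set and the credibility of the blind, in a trial of 45 participants with a single tissue readout as its primary endpoint.

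**Working it through.** **1. The plan's own figure.** Section 13.3 gives 14 placebo and 28 erlotinib participants for a 1 SD effect, two-sided 0.05, power 0.85.

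- Noncentrality = 1/√(1/14 + 1/28) = 3.06.
- Power is 0.846 by the noncentral t and 0.863 by the normal approximation, so the figure reproduces.
- With 5% dropout, 14/0.95 and 28/0.95 round up to 15 and 30. This point disputes none of these numbers.

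**2. What a level can show.** The half-life is 10-12 h (section 2.2). Assume simple one-phase decay: fraction left = 2^(−time/half-life).

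- Day 8 pre-dose, about 168 h after dose 1: 168/12 = 14 to 168/10 = 16.8 half-lives. About 0.006% to 0.001% is left, so this sample cannot confirm the first dose.
- Surgery, 9-18 h after the last dose: 2^(−9/12) = 0.59 down to 2^(−18/10) = 0.29. A level of this order shows active assignment. An undetectable one strongly suggests placebo, but also fits an erlotinib participant who skipped the last dose.

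The level therefore tests one dose, in one arm.

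**3. How large the bias could be.** Let a fraction q of each arm silently miss the last dose, and let them differ from takers by s SD in the marker for reasons unrelated to drug. Let takers on erlotinib have an effect δ, and non-takers none. Assume the level flags every erlotinib non-taker. Erlotinib minus placebo is then:

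- as-randomized: [(1−q)δ + qs] − qs = (1−q)δ
- non-takers removed from both arms: δ
- non-takers removed from erlotinib only: δ − qs

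The part due to one-sidedness is −qs, and its sign depends on how non-takers differ. The documents give neither q nor s, so both are assumed. The table takes δ = 0 and 15:30 enrolled; type I error is from 40,000 simulated trials per setting.

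| q | Expected flagged, erlotinib (30q) | Expected undetected, placebo (15q) | Bias (SD), s = 0.5 to 1 | Type I error, s = 0.5 to 1 |
|---|---|---|---|---|
| 5% | 1.5 | 0.75 | 0.025 to 0.05 | 0.052 to 0.055 |
| 10% | 3 | 1.5 | 0.05 to 0.10 | 0.052 to 0.062 |
| 20% | 6 | 3 | 0.10 to 0.20 | 0.061 to 0.091 |

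The lost participants matter little for power at 1 SD: 0.871 at 15:30, 0.858 at 15:27, 0.841 at 15:24.

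**The case against.** The strongest reply is that the statistical section already settles the matter. Under 13.6 and 13.8 compliance does not enter the primary analysis, and no treated eligible participant leaves it because of a drug level. If that section governs, the bias above is zero. This limits the point but does not remove it. Section 5.7.1 still says who is evaluable, and 8.4 makes use of data subject to compliance requirements and refers to 13.4, which states none. Staff following section 5 and analysts following section 13 would form different sets.

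Three stronger readings are tempting and not supported.

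- A reader might infer that one-sided exclusion inflates the effect by 5-11%, because a 1 SD effect in takers is diluted to 0.90-0.95 SD as randomized and returns to 1.0 SD after exclusion. In that model s = 0, and removing non-takers from both arms also gives 1.0 SD. The gain comes from a completers-only analysis, not from the one-sided measure.
- A reader might infer that every assignment is revealed. An undetectable level does not prove placebo.
- A reader might infer that the blind fails before the tissue is read. No section gives the order of the drug assay and the tissue reading. Blood ships after the participant has finished the study (10.3.1), the blood goes to the 3P Laboratory while tissue markers are read in the TRIP Laboratory (10.1), and no section sends levels to sites or tissue readers. Against that, 7.5 lets tissue requests wait up to 2 months and nothing withholds the levels. Unblinding of site or tissue-reading staff is a risk, not something shown.

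It is also fair that the level is the only objective check of intake in a self-administered study, and that 5.7.2 gives no rule by which it overrides a tablet count.

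**Conclusion.** The point holds in limited form. Read together, 5.7.1 and 5.7.2 let a measure that works in one arm, for the last dose only, and only with the code in hand, influence who is evaluable for the primary endpoint. That contradicts 13.6 and 13.8. Separately, the statement in 6.9 about assay staff cannot be true of the pharmacokinetic laboratory.

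The asymmetry follows from the text. Its numerical effect does not. It is nil if section 13 governs. If section 5 governs, it rests on assumed non-taking rates, an assumed difference between non-takers and takers, and full detection in the erlotinib arm. At 5-10% it is modest, and it becomes material only towards 20%. The direction of any bias from unblinded compliance judgements is not established. The plan should be amended because two of its rules conflict and the repair is cheap, not because a large bias has been demonstrated.

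**What to change.** 1. Reconcile 5.7.1 with 13.6 and 13.8. Make the as-randomized set of treated participants primary in both places, and label any completer or evaluable set as supporting only. This comes first: removing drug levels alone would leave 5.7.1 excluding participants who stop dosing early, whom 13.8 keeps.
2. Remove drug levels from the 5.7.2 judgement wherever it affects evaluability. Use tablet count and questioning alike in both arms, and align 13.6, which names pill counts only. Keep levels for the pharmacokinetic objective and the dose-received supporting analysis in 13.4.
3. In 6.9, name the pharmacokinetic laboratory as effectively unblinded. State that its results are held from site, coordinating-center, tissue-reading and evaluability staff until tissue quantification and the analysis sets are locked.

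The cost is wording in four sections and a later release of results. The small downside is that drug level no longer contributes to the compliance classification. The pharmacokinetic objective loses nothing.
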